12.13 Causality Assessment/Association with the Study Medication

Every effort will be made to obtain all the required information to determine whether the Adverse Event is related or unrelated to the study procedure or Investigational Medicinal Product (causal relationship).

Protocol for clinical study of Brequinar

Protocol No.: 21-VIN-0372

Version No.: 2.1; Dated: 29 Dec 2021

Supersedes: 02; Date of Supersedes: 30 Sep 2021

In terms of relationship

Causality term	Assessment criteria
Definite*	
 • Event or laboratory test abnormality, with plausible time relationship to drug intake • Cannot be explained by disease or other drugs • Response to withdrawal plausible (pharmacologically, pathologically) • Event definitive pharmacologically or phenomenologically (i.e. an objective and specific medical disorder or a recognised pharmacological phenomenon) • Re-challenge satisfactory, if necessary
Probable*	
 • Event or laboratory test abnormality, with reasonable time relationship to drug intake • Unlikely to be attributed to disease or other drugs • Response to withdrawal clinically reasonable • Re-challenge not required
Possible*	
 • Event or laboratory test abnormality, with reasonable time relationship to drug intake • Could also be explained by disease or other drugs • Information on drug withdrawal may be lacking or unclear
Unlikely [#]	
 • Event or laboratory test abnormality, with a time to drug intake that makes a relationship improbable (but not impossible) • Disease or other drugs provide plausible explanations
Not Related [#]	
 • The AE is clearly NOT related to the study treatment

Note: [#]Unlikely and Not Related will be considered as Not Related.

*Definite, Probable and Possible will be considered as Related.

12.14 Outcome Categories

The outcome of adverse event will be categorized as following:

Protocol for clinical study of Brequinar
 Protocol No.: 21-VIN-0372
 Version No.: 2.1; Dated: 29 Dec 2021
 Supersedes: 02; Date of Supersedes: 30 Sep 2021

- Recovered/ Resolved
- Recovering/ Resolving
- Recovered with sequelae/ Resolved with sequelae
- Not recovered/ Not Resolved
- Fatal
- Unknown

13.0 SAMPLE PROCESSING AND TRANSFER PROCEDURES

Clinical Laboratory Samples:

All clinical laboratory blood and urine samples will be transferred to the central laboratory in controlled temperature and in pre validated laboratory kits which will be supplied to all the sites by the central laboratory. In case of emergency, samples can be sent to local laboratory for safety assessment at the discretion of the investigator.

Pharmacokinetic (PK) samples:

After collection of PK blood samples from all subjects at each time point, they will be centrifuged at 4000 RPM for 10 minutes at 5 ± 3 °C to separate plasma. For precaution purpose, the blood samples will be kept on wet ice bath (below 10 °C) both before centrifugation and after separation.

The separated plasma will be transferred to pre-labeled polypropylene tubes in 2 aliquots:

For Brequinar and Dipyridamol PK:

Aliquot 1: Approximately 1.7 mL of plasma

Aliquot 2: Approximately 1.2 mL of plasma

Aliquot will be stored upright in a box containing dry ice or in a freezer at a temperature -15 °C or colder for interim storage at different investigator sites until shipment to Veeda Clinical Research Ltd., Ahmedabad, for analysis.

Note: Entire activity from blood sample collection to storage in a freezer should be completed within 60 minutes time.

During shipment the samples will be packed in thermocol boxes containing adequate amount of dry ice. The temperature will be monitored using calibrated data logger during shipment. Samples will then be stored at -78 \pm 8 °C until completion of analysis at Veeda Clinical Research Ltd., Ahmedabad.

Protocol for clinical study of Brequinar

Protocol No.: 21-VIN-0372

Version No.: 2.1; Dated: 29 Dec 2021

Supersedes: 02; Date of Supersedes: 30 Sep 2021

Shipment for each aliquot will be carried out separately.

A designated person from bioanalytical department will receive the samples at Veeda Clinical Research Ltd., Ahmedabad or designate on arrival. The condition of the samples will be examined on arrival at Veeda Clinical Research Ltd., Ahmedabad and if any of the samples are not in a frozen condition, clinical facility and\or Sponsor will be informed for the same. After receiving the samples at Veeda Clinical Research Ltd., Ahmedabad, the samples will be stored at -78 ± 8 °C until completion of analysis.

Note: Samples of patients enrolled in Arm 3 (SOC + Placebo) of each cohort will not be analysed.

qPCR Samples

The qPCR samples are to be collected, processed, stored, and shipped as per the instructions in the Laboratory Manual.

14.0 BIOANALYTICAL PROCEDURES

The Bioanalytical procedures will be performed at Bioanalytical facility of Veeda Clinical Research Ltd. Validated analytical method will be used for the PK analysis of the plasma samples.

14.1 Method Validation

Bioanalytical method will be validated at Veeda clinical research Ltd., which is in accordance with the regulatory guidelines on validation of bioanalytical methods.

Method validations of Brequinar and Dipyridamol will be carried out by using analytical method developed at Veeda Clinical Research Ltd. This analytical methods will be validated for the sensitivity, specificity, matrix effect, linearity, ruggedness, accuracy and precision (repeatability and reproducibility), percent recovery and stability of samples (bench-top stability, autosampler stability, short-term, long-term stability of stock solution and internal standard) and effect of concomitant medications, if any.

14.2 Assay of Samples

The Brequinar and Dipyridamol will be quantified using a validated method. All available plasma samples of all subjects in the study will be analyzed as per approved protocol irrespective of withdrawn or dropped out from the study.

The analysis of subject's samples will be done using calibration curve with quality control samples, distributed throughout each batch. The details for the preparation of the calibration curve and quality control samples and the analytical batch acceptance criteria will be discussed in the respective in-house procedure. The analyst will not have access to the randomization schedule until analysis is completed.

Note: Samples of patients enrolled in Arm 3 (SOC + Placebo) of each cohort will not be analysed.

Protocol for clinical study of Brequinar
Protocol No.: 21-VIN-0372
Version No.: 2.1; Dated: 29 Dec 2021
Supersedes: 02; Date of Supersedes: 30 Sep 2021

14.3 Incurred Study Sample Re-analysis

Incurred Study Sample Re-analysis will be performed to ensure method reproducibility as per SOP (VIN-BRD-092).

15.0 STATISTICAL ANALYSIS

15.1 Statistical Analysis Plan

A statistical analysis plan (SAP) will be prepared and finalized prior to the database lock. Detailed description of the statistical methodology, population and handling of missing data will be described in this document. Mock tables and listings will be provided with the SAP.

15.2 Sample Size Estimation

There is no prospective powering in this study. The sample size was chosen to provide an adequate number of subjects to provide reasonable safety and efficacy data for this type of study.

15.3 Study Population for Analysis

➤ Intent-to-treat population:

Intent-to-treat (ITT) analysis set will include all the subjects who undergo randomization.

➤ Safety Population:

The safety population will include all randomized subjects who receive at least one dose of the study product.

15.4 Analysis of Efficacy Data

All statistical analysis will be done using SAS® Version 9.4 or higher (SAS Institute Inc., USA).

For continuous variables, the summary statistics will be the number of observations, mean, standard deviation, median, minimum and maximum values. Categorical values will be summarized using frequencies and percentages.

Primary Endpoints:

- Frequencies of grade 3 and 4 toxicities and serious adverse events (SAEs) considered by the investigator to be related to the combination, brequinar alone or placebo alone.

Because the primary study endpoint is a safety parameter no formal statistical testing will be performed for this parameter.

Protocol for clinical study of Brequinar
 Protocol No.: 21-VIN-0372
 Version No.: 2.1; Dated: 29 Dec 2021
 Supersedes: 02; Date of Supersedes: 30 Sep 2021

Secondary Endpoints:

For subjects treated with the brequinar-dipyridamole combination compared to subjects treated with the brequinar and to subjects treated with the placebo combination through Day 29, to determine:

- SARS-CoV-2 levels through Day 29 and at days 4, 8, 12, 15, 22, and 29 will be analyzed using analysis of covariance (ANCOVA) test;
- Time to symptom improvement through Day 29 will be analyzed using Kaplan-Meier time-to-event analysis;
- Percentage of subjects requiring hospital admission/re-admission as an in-patient for >24 hours through Day 29 will be analyzed using Fisher exact / chi square test;
- Percentage of subjects requiring medical attended visits, e.g., hospitalization, emergency room visits, Urgent Care/Family Doctor visits through Day 29 will be analyzed using Fisher exact / chi square test ;
- Percentage of subjects requiring supplemental support such as oxygen through Day 29 will be analyzed using Fisher exact / chi square test.

Exploratory Endpoints:

- Brequinar's pharmacokinetic profile in a subset of patients that have received brequinar as a part of therapy and have consented to provide PK samples will be analyzed descriptively.

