9.0 STUDY PROCEDURE

9.1 Study Design

The first part of the study will be a phase II, randomized, assessor-blind, multicenter, multi-dose, placebo-controlled study in approximately 64 subjects with mild to moderate COVID-19 infection confirmed by a positive SARS-CoV-2 RT-PCR qualitative test /rapid antigen test and who have at least mild to moderate signs and/or symptoms ongoing at study entry.

Approximately 32 subjects (50% of subjects per arm per cohort) at selected sites will be invited to participate in the “PK” arm of the study until approximately 8 subjects in each cohort have been recruited after providing written informed consent for the same. PK includes brequinar and dipyridamole plasma concentrations.

If a particular cohort meets study stopping criteria (as defined in section “Stopping Criteria”) or is found to be unsafe by DSMB members, then the study will not proceed with enrollment of subsequent cohorts.

An expansion cohort of approximately 48 subjects will be added to the cohort with the highest brequinar dose that meets safety criteria.

Safety data of cohort 1 to cohort 4 (or highest dose cohort evaluated) will be submitted to the regulators and their approval will be obtained prior to commencing recruitment in the expansion cohort.

All subjects will receive SOC as per relevant guidelines for treatment of patients with mild to moderate COVID-19 infection.

Subjects will be randomized to one of the following cohorts in Part 1:

Cohort 1:

- Arm 1: 5 days of standard of care (SOC) + brequinar 50 mg OD + dipyridamole 75 mg TID (N = 8)
- Arm 2: 5 days of SOC + brequinar 50 mg OD (N = 4).
- Arm 3: 5 days of SOC + brequinar placebo 50 mg OD (N = 4).

Cohort 2:

If the 50 mg brequinar OD + dipyridamole 75 mg TID meets safety criteria as pre-defined in the protocol the brequinar dose will be escalated to 100 mg.

- Arm 1: 5 days of standard of care (SOC) + brequinar 100 mg OD + dipyridamole 75 mg TID (N = 8)
- Arm 2: 5 days of SOC + brequinar 100 mg OD (N = 4).
- Arm 3: 5 days of SOC + brequinar placebo 100 mg OD (N = 4).

Cohort 3:

If the 100 mg brequinar OD + dipyridamole 75 mg TID meets safety criteria as pre-defined in the protocol the brequinar dose will be escalated to 150 mg:

Protocol for clinical study of Brequinar

Protocol No.: 21-VIN-0372

Version No.: 2.1; Dated: 29 Dec 2021

Supersedes: 02; Date of Supersedes: 30 Sep 2021

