- Arm 1: 5 days of standard of care (SOC) + brequinar 150 mg (100 mg + 50 mg) OD + dipyridamole 75 mg TID (N = 8)
- Arm 2: 5 days of SOC + brequinar 150 mg (100 mg + 50 mg) OD (N = 4)
- Arm 3: 5 days of SOC + brequinar placebo 150 mg (100 mg + 50 mg) OD (N = 4).

Cohort 4:

If the 150 mg brequinar OD + dipyridamole 75 mg TID meets safety criteria as pre-defined in the protocol the brequinar dose will be escalated to 200 mg:

- Arm 1: 5 days of standard of care (SOC) + brequinar 200 mg (100 mg +100 mg) OD + dipyridamole 75 mg TID (N = 8)
- Arm 2: 5 days of SOC + brequinar 200 mg (100 mg +100 mg) OD (N = 4)
- Arm 3: 5 days of SOC + brequinar placebo (100 mg + 100 mg) OD (N = 4).

Expansion Cohort:

Approximately forty-eight (48) subjects will be added to the cohort with the highest brequinar dose that meets safety criteria in a 2 : 1 ratio of active treatment (approximately 32 in SOC + brequinar + dipyridamole treated and 16 in SOC + brequinar monotherapy group). Additional sites may be added if required to meet enrollment of the expansion cohort in an efficient manner.

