9.7 Patient identification and Randomisation

Randomization will be carried out using SAS® (SAS Institute Inc., USA) version 9.4 or higher. Randomization will be done in blocks using PROC PLAN such that the design is unstructured. The treatment allocation will be determined according to the randomization schedule and randomization schedule will be done per cohort.

Screening and Randomization Numbering

Each subject will be assigned a unique number that will serve to identify laboratory specimens and all documents, and if randomized throughout the study. If a subject fails to qualify for allocation to the study i.e. is a screen failure, the subject's unique number will not be used for another subject.

Screening number will be a combination of center number, project number and subject number. The center number will be assigned by Veeda to the investigative site (e.g. A, B, C, D) and subsequent sites are assigned consecutive alphabet numbers. Upon signing the informed consent form, the subject will be assigned a screening number by the Investigator. At each site the first subject consented is assigned screening number e.g. A-21-0372-001, and subsequent subjects are assigned consecutive numbers (e.g., the second subject consented is assigned screening number A-21-0372-002, the third subject is assigned screening number A-21-0372-003). Once a screening number is assigned to a subject, that number will not be reused.

If the subject is deemed eligible for enrollment into the study and will commence dosing, then a randomization number will be assigned via IWRS as defined in the randomization plan. Subjects will be randomized with the next qualifying subject given the next available randomization number.

A source document maintained at the site will link the screening number to the randomization assignment number (once assigned) and the same will be reflected in screening and enrollment log of Investigator site file.

The assigned subject number will be recorded in the CRF of the subject.

Protocol for clinical study of Brequinar

Protocol No.: 21-VIN-0372

Version No.: 2.1; Dated: 29 Dec 2021

Supersedes: 02; Date of Supersedes: 30 Sep 2021

The personnel involved in dispensing of study drug and verification of dispensed study drugs will be accountable for ensuring compliance to randomization schedule.

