11.0 EFFICACY ASSESSMENT

Efficacy will primarily be assessed by reduction in SARS-CoV-2 RNA levels as measured by the quantitative RTPCR test for SARS COV2 in brequinar-dipyridamole treated subjects compared to brequinar-only and placebo-treated subjects through Day 29.

Symptom improvement will be defined in the SAP. Clinical improvement for the ordinal scale will be defined as defined as a 2-point or greater improvement on an 8-point WHO ordinal scale in every subject measured on each designated day (i.e Screening, Days 1, 4, 8, 12, 15, 22, 29), until Day 29 from the date of randomization. This scale has been used in the current COVID-19 outbreak.

Ordinal Scale for Clinical Improvement

Patient State	Descriptor	Score
Uninfected	No clinical or virological evidence of infection	0
Ambulatory	No limitaion of activities	1
	Limitation of activities	2
Hospitalized Mild disease	Hospitalized, no oxygen therapy	3
	Oxygen by mask or nasal prongs	4

Protocol for clinical study of Brequinar

Protocol No.: 21-VIN-0372

Version No.: 2.1; Dated: 29 Dec 2021

Supersedes: 02; Date of Supersedes: 30 Sep 2021

Hospitalized Severe Disease	Non-invasive ventilation or high-flow oxygen	5
	Intubation and mechanical ventilation	6
	Ventilation + additional organ support – pressors, RRT, ECMO	7
Dead	Death	8

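### The expansion cohort has no placebo arm, yet Section 15.4 neither limits placebo comparisons to Part 1 nor includes a cohort or stage term

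*Combined protocol and SAP*

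**What the plan says.** All references are to protocol version 2.1.

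- **Design (9.1).** Up to four sequential Part 1 cohorts, each 8 combination, 4 brequinar alone and 4 placebo. The expansion then adds "approximately 32 in SOC + brequinar + dipyridamole treated and 16 in SOC + brequinar monotherapy group", with no placebo subjects, at the highest dose that meets the safety criteria.
- **Timing and sites (9.1, 9.2).** Part 1 safety data go to the regulators and "their approval will be obtained prior to commencing recruitment in the expansion cohort". The DSMB also meets between Part 1 and the expansion. "Additional sites may be added if required to meet enrollment of the expansion cohort in an efficient manner".
- **Randomisation (9.7).** "The treatment allocation will be determined according to the randomization schedule and randomization schedule will be done per cohort".
- **Analysis set (15.3).** The ITT "analysis set will include all the subjects who undergo randomization".
- **Analysis (15.4).** Combination subjects are compared with brequinar subjects and "to subjects treated with the placebo combination through Day 29". For viral load, "SARS-CoV-2 levels through Day 29 and at days 4, 8, 12, 15, 22, and 29 will be analyzed using analysis of covariance (ANCOVA) test". Kaplan-Meier is named for the symptom endpoint, and Fisher or chi-square tests for the percentage endpoints. No covariate, cohort, stage or dose term is named.
- **Role of the contrast (11.0).** Efficacy rests mainly on viral load in combination subjects "compared to brequinar-only and placebo-treated subjects through Day 29".
- **Deferral and status (15.1, 15.2, 3.1).** Methods and populations are left to a SAP that is not among the documents. The study is not powered, and all testing is called exploratory.

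**The concern.** Placebo subjects exist only in Part 1, while a large share of the combination arm would be recruited later and perhaps at other sites. Randomisation does not protect a comparison between expansion subjects and Part 1 placebo subjects. If the circulating variant, vaccination, standard of care or site mix changes between stages, that change is read as a drug effect.

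A general instruction to adjust for cohort would not settle it. Section 9.1 describes the expansion as an addition to the highest-dose cohort, so the natural coding gives both groups one cohort level, and part of the bias stays. At stake is the placebo half of what Section 11.0 calls the main efficacy assessment, together with the symptom, hospitalisation, medical-visit and oxygen endpoints.

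**Working it through.** **Counts.** The plan's totals reproduce: 4 × (8 + 4 + 4) = 64 and 32 + 16 + 0 = 48. With four cohorts the arms are combination 4 × 8 + 32 = 64, brequinar 4 × 4 + 16 = 32, placebo 4 × 4 = 16.

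**Bias per unit stage shift, combination minus placebo.**

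- *No cohort term:* the weight is the expansion share of the combination arm, 32 / (8k + 32) for k Part 1 cohorts.
- *Expansion merged with the top cohort:* that stratum has 60 active and 4 placebo subjects, so its information on the placebo contrast is 4 × 60 / 64 = 3.75. Each other cohort gives 4 × 12 / 16 = 3. In the merged stratum 32/40 = 0.8 of the combination subjects (and 16/20 = 0.8 of the brequinar subjects) are shifted. The weight is 0.8 × 3.75 / (3.75 + 3(k − 1)). For k = 4 this is 0.8 × 3.75 / 12.75 = 0.235.
- *Separate expansion level, or Part 1 only:* 0.

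| Part 1 cohorts | Combination v placebo | No term | Merged | Separate or Part 1 only |
|---|---|---|---|---|
| 4 | 64 v 16 | 0.50 | 0.24 | 0 |
| 3 | 56 v 12 | 0.57 | 0.31 | 0 |
| 2 | 48 v 8 | 0.67 | 0.44 | 0 |
| 1 | 40 v 4 | 0.80 | 0.80 | 0 |

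For combination minus brequinar the bias is 0 in every row, because the ratio is 2:1 in every stage. Read by dose instead, the expanded dose is 40 v 4, of which only 8 v 4 is concurrent.

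**Standard error of the placebo contrast** (SD units, before baseline adjustment, four cohorts).

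- Pooled: √(1/64 + 1/16) = 0.280.
- Part 1 only, with cohort: √((1/8 + 1/4)/4) = 0.306, or +10%.
- Separate expansion level: 0.298, or +6%. Here the Part 1 combination mean (variance 1/32) gains from an indirect estimate through brequinar (variance 1/16 + 1/32 + 1/16 = 5/32), so the variance is 1/(32 + 6.4) + 1/16 = 0.0885.

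**Illustrative rejection rates.** The documents give no drift size, SD, baseline correlation or significance level, so all of these are assumed. The setting is four cohorts, no true effect, nominal two-sided 5%, ANCOVA with baseline viral load, SD 1.5 log10 and correlation 0.5, by simulation.

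| Model | Stage shift leaves baseline unchanged: 0.5 / 1.0 / 1.5 log10 | Baseline shifts equally: 0.5 / 1.0 / 1.5 log10 |
|---|---|---|
| No cohort term | 10% / 23% / 42% | 6% / 9% / 12% |
| Expansion merged with top cohort | 6% / 9% / 13% | 5% / 5% / 7% |
| Separate level or Part 1 only | 4–6% | 4–6% |

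In the no-term model the mean bias is 0.25 / 0.50 / 0.75 log10 with baseline unchanged and 0.13 / 0.23 / 0.30 with an equal shift. Varying SD over 1.0–2.0 (correlation 0.5) and correlation over 0.3–0.7 (SD 1.5), the no-term rates run 8–15%, 16–42% and 28–71% with baseline unchanged, and 5–8%, 7–13% and 9–16% with an equal shift.

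**Percentage endpoints.** There is no baseline covariate to absorb drift. If the event rate is assumed to be 20% in Part 1 and 10% in the expansion, the pooled combination rate is (20% + 10%)/2 = 15% against 20% on placebo, with no drug effect. Fisher's test on 64 v 16 would then reject 6.6% of the time, against 3.1% with 20% throughout.

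**The case against.** The strongest reply is that nothing here declares a pooled analysis. Section 15.1 assigns methods and populations to a SAP, which could restrict the placebo contrast. Section 9.1 applies the placebo-controlled label to the first part of the study only. The synopsis says results are presented by group, which might mean by cohort and arm. The stated purpose in Section 5.6, whether dipyridamole improves on brequinar, is the unbiased contrast. The larger rejection rates need large assumed shifts that leave baseline viral load untouched, and the binary example stays close to nominal. The primary endpoint is safety, nothing is powered, and dose selection rests on safety criteria.

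Much of this stands and limits the severity. It does not close the gap. Section 15.4 already chooses a method for each endpoint, and with the all-randomised set of 15.3 those methods give a non-concurrent placebo comparison. The word group is undefined and sets no model term, and by-dose presentation makes the imbalance worse at the expanded dose. The bias weights follow from the arm counts alone, and a descriptive estimate is biased as much as a tested one. The choice between Part 1 only and a separate expansion level is partly preference. Both are unbiased, but the second needs treatment effects to be additive across stages.

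**Conclusion.** The concern holds. As written, Sections 15.3 and 15.4 allow a combination-versus-placebo comparison in which 50% of the combination arm (57%, 67% or 80% with fewer cohorts) and none of the placebo arm come from a later stage. The same fraction of any stage shift passes into the unadjusted estimate. Merging the expansion with its dose cohort leaves 0.24 to 0.80 of it.

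The weights assume the planned arm sizes and an additive shift common to all arms. The rejection rates rest on assumed drift, SD and correlation and are illustrations only. The pooled contrast also averages over doses (40 of 64 at the expansion dose), which is a question of what is being estimated and not of confounding. It should be fixed before database lock. The consequence otherwise is a misleading exploratory efficacy estimate, not a failed confirmatory test or a flaw in the escalation rule.

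**What to change.** State in Section 15.4 and in the SAP, before database lock:

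1. Placebo contrasts use only concurrently randomised Part 1 subjects. The ANCOVA has cohort as a factor and baseline log10 viral load as a covariate. Binary endpoints use an exact Cochran-Mantel-Haenszel test stratified by cohort, and the time-to-event comparison is stratified likewise.
2. Combination versus brequinar uses all subjects, with the expansion as its own stratum, distinct from the Part 1 cohort at the same dose.
3. An all-subject model with a separate expansion level may serve as a sensitivity analysis for the placebo contrast, with its additivity assumption stated.
4. Any comparison of expansion subjects with Part 1 placebo subjects, including 40 v 4 at the expansion dose, is labelled non-randomised.

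The cost is wording and some precision, with no extra patients. Moving from pooled to Part 1 only raises the standard error from 0.280 to 0.306 SD with four cohorts (+10%), 0.318 to 0.354 with three (+11%), 0.382 to 0.433 with two (+13%) and 0.524 to 0.612 with one (+17%). The loss is small because the placebo count limits precision either way.

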9.6 Sample Size

No statistical powering has been performed for this study. The number of subjects is designed to provide information on the safety, tolerability, and efficacy of the IMP tested in this study. In Part 1, approximately 64 subjects will be randomized to up to 4 cohorts of 5 consecutive days of one of the following regimens in addition to SOC in 2:1:1 ratio as shown below:

Treatment Arm ^a	Day 1	Day 2	Day 3	Day 4	Day 5
Brequinar + Dipyridamole (N=8)	BRQ XX mg OD DPY 75 mg TID				
Brequinar (N=4)	BRQ XX mg OD				
Placebo (N=4)	PBO XX mg OD				

Protocol for clinical study of Brequinar

Protocol No.: 21-VIN-0372

Version No.: 2.1; Dated: 29 Dec 2021

Supersedes: 02; Date of Supersedes: 30 Sep 2021

^aAll subjects will also received standard of care (SOC).

The brequinar dose will start at 50 mg and may be escalated to 100 mg, 150 mg, and 200 mg if safety criteria are met for each cohort (see Safety Criteria below).

The hospital pharmacist is to be unblinded. Bulk supplies of investigational medicinal product (IMP) of brequinar 50 mg, brequinar 100 mg, dipyridamole 75 mg, brequinar placebo 50 mg and brequinar placebo 100 mg will be supplied to the unblinded hospital pharmacist.

The unblinded hospital pharmacist is to prepare the assigned IMP for each individual subject at that institution and create an appropriately labeled bottle/zip lock bag of study medication sufficient for a 5-day treatment course. The randomization assignment will be provided via an IWRS.

Alternatively, the hospital pharmacist and study team may decide to distribute IMP on a daily basis for 5 days for brequinar and dipyridamole while the subject is hospitalized, depending on the most convenient method.

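### Randomisation is separate for each cohort, but section 15.4 names no cohort term or stratum; adding one to the viral-load ANCOVA would gain precision at almost no cost

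*Combined protocol and SAP*

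**What the plan says.** All references are to protocol Version 2.1.

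- **Randomisation (9.7).** It is blocked, and "randomization schedule will be done per cohort".
- **Cohorts (9.1, 9.6).** Up to four cohorts open in sequence at brequinar 50, 100, 150 and 200 mg, each step conditional on the safety of the one before. Allocation is to combination, brequinar and placebo, in "addition to SOC in 2:1:1 ratio as shown below", that is 8:4:4 per cohort.
- **Expansion (9.1).** About 48 more subjects join at the highest dose that meets the safety criteria: "approximately 32 in SOC + brequinar + dipyridamole treated and 16 in SOC + brequinar monotherapy group". There is no placebo.
- **Comparisons (15.4).** They are framed by treatment alone: "For subjects treated with the brequinar-dipyridamole combination compared to subjects treated with the brequinar and to subjects treated with the placebo combination".
- **Methods (15.4).** For viral load, "SARS-CoV-2 levels through Day 29 and at days 4, 8, 12, 15, 22, and 29 will be analyzed using analysis of covariance (ANCOVA) test". For symptoms, "Time to symptom improvement through Day 29 will be analyzed using Kaplan-Meier time-to-event analysis". The binary endpoints get a Fisher exact or chi-square test. No cohort factor, dose factor or stratum is named for any of them.
- **Detail and status.** Section 15.1 leaves full methodology to a SAP to be finalised before database lock. Section 15.2 says the trial is not prospectively powered. The synopsis calls all testing exploratory and descriptive.

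**The concern.** Combination against brequinar alone is the contrast that answers the stated purpose of the study in section 5.6: whether dipyridamole improves brequinar's antiviral activity. The design balances cohort between these two arms. Differences between cohorts in dose, season, circulating variant or site mix therefore do not enter the estimate. A model without cohort does not know this. It leaves the between-cohort variation in the residual and reports more uncertainty than the estimate has.

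The price is a wider interval, a test below its nominal level and lost power. In an unpowered trial the estimate and its interval are the result, so an interval of the right width is worth having.

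**Working it through.** **1. Counts.** Part 1: 4 × (8 + 4 + 4) = 64, which matches "placebo-controlled study in approximately 64 subjects with mild to moderate COVID-19 infection". Expansion: 32 + 16 = 48, which also matches. Combination against brequinar over the whole trial is (4 × 8 + 32) = 64 against (4 × 4 + 16) = 32. The plan states no power, effect size or SD to reproduce.

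**2. Is the pooled estimate biased?** If the expansion is counted with cohort 4, the combination shares by cohort are 8/64, 8/64, 8/64, 40/64 = 0.125, 0.125, 0.125, 0.625. The brequinar shares are 4/32, 4/32, 4/32, 20/32, which are the same. The pooled difference in means is therefore the weighted average of the same-dose differences, and cohort effects cancel. With within-cohort SD σ:

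- Pooled: σ√(1/64 + 1/32) = 0.217σ.
- By cohort: σ/√Σ[n₁n₂/(n₁ + n₂)] = 0.217σ.

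The true precision is the same either way. Only the reported standard error can differ.

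**3. How far is the reported standard error off?** Let τ² be the between-cohort variance divided by the within-cohort variance, and w the share of the 96 subjects in each stratum. With random cohort effects, the reported SE without cohort is too large by about √[1 + (1 − Σw²)τ²], where τ² = share/(1 − share).

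- Five strata (four of 12, one of 48): Σw² = 4 × 0.125² + 0.5² = 0.3125, so the multiplier of τ² is 0.6875.
- Four strata (three of 12, one of 60): Σw² = 3 × 0.125² + 0.625² = 0.4375, so the multiplier is 0.5625.

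Example, 20% share and five strata: τ² = 0.25 and √(1 + 0.6875 × 0.25) = 1.08.

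The shares below are assumptions. Test level and power come from simulation (least squares, five strata, no baseline covariate, two-sided 5%). The 0.6 SD is in units of the total outcome SD.

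| Cohort share of variance | SE excess, five strata | SE excess, four strata | Actual level of 5% test | Power at 0.6 SD, without / with cohort |
|---|---|---|---|---|
| 0% | 0% | 0% | 5.0% | 78 / 78 |
| 5% | 2% | 1% | about 4.5% | 79 / 80 |
| 10% | 4% | 3% | about 4.2% | 81 / 83 |
| 20% | 8% | 7% | about 3.6% | 82 / 87 |
| 30% | 14% | 11% | about 2.8% | 85 / 91 |

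**4. Does a baseline covariate change the mechanism?** A separate simulation used an ANCOVA with one baseline covariate, four strata and fixed cohort means whose subject-weighted spread was τ = 0.5. The estimate's actual SD was 0.220. The reported SE was 0.243 without cohort and 0.217 with it, an excess of 12%. This exceeds the 7% in the table because τ is here the spread realised among these subjects, so the factor is √(1 + τ²) = √1.25 = 1.12. The direction is the same.

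**5. Symptom time.** Section 15.4 names no between-arm test. If a log-rank test were used, rejection at a hazard ratio of 1.8 would be 54% unstratified against 69% stratified for a between-cohort SD of 0.5 in log rate. With no cohort differences it would be 77% against 75% (600 runs per setting).

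**The case against.** Section 15.4 gives one-line method labels, not models. Its ANCOVA lists no covariate at all, not even baseline viral load, and 15.1 sends the detail to a SAP whose text is not among the documents. A reader might infer that the plan pools cohorts and leaves cohort out. The documents do not say so; they only fail to say that it is in. This stands, and the point is worded accordingly. It does not remove the value of naming the term now, since 15.1 lets the SAP be settled as late as database lock.

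A reader might also infer that same-dose comparisons are discarded. They are not: with a constant 2:1 ratio the pooled difference is the weighted same-dose difference. Nor can the planned error bars for symptom time be called too wide, because no treatment contrast is planned there to have one.

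The size rests on assumed variance shares and is small at the low end. A baseline covariate might absorb some of the cohort variation. Counting the expansion as part of the highest-dose cohort, which 9.1 also allows, makes the excess a little smaller. Testing is exploratory and unpowered, and the error is on the conservative side. All of this stands and limits the weight of the point.

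**Conclusion.** The point holds as a recommendation on precision. Randomisation is by cohort, 15.4 names no cohort term, and if cohorts differ, leaving cohort out overstates the standard error for combination against brequinar by about 2 to 14% over assumed variance shares of 5 to 30% (1 to 11% with four strata). Power at 0.6 SD falls by 1 to 6 points. If cohorts do not differ, nothing is lost either way.

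These figures assume a two-sided 5% test, all four cohorts and the full expansion enrolled, and random cohort effects of the stated size. The documents supply no SD with which to narrow the range.

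It would be wrong to read this as bias or as an invalid analysis: the estimate is unbiased and the test errs towards caution. The unbiasedness argument covers combination against brequinar only. It does not carry over to placebo, which has no subjects in the expansion.

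**What to change.** In 15.4, and in the SAP:

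1. Include cohort as a fixed factor in the viral-load ANCOVA, with Part 1 cohorts 1 to 4 and the expansion as separate levels.
2. If a log-rank or Cox comparison between arms is used for time to symptom improvement, stratify it by the same levels.
3. Optionally, give Mantel-Haenszel risk differences by cohort for the binary endpoints where there are enough events.

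The cost is wording and up to 4 degrees of freedom out of 96 subjects in this contrast. No change to conduct, data collection or sample size is needed.
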